Appendix G Schedule 2—Laboratory procedures for HIV-1–infected participants

				J 1								
				Visit:	#.X ⁵	Visit:	31	32	33	34	35	
						Days:	D28	D42	D56	D84	D168	
						Weeks after	W4	W6	W8	W12	W24	
						diagnosis ⁷ :						
			Tube	Tube size								
Procedure	Ship to ¹	Assay location ²	Type ³	(vol. capacity) ³								Total
BLOOD COLLECTION												
Screening or diagnostic assays		2								÷		
HIV diagnostics	UW-VSL / Peru CTU Laboratory / CADIG-Immunodiagnostic Lab (INI-FIOCRUZ)	UW-VSL / Peru CTU Laboratory / CADIG-Immunodiagnostic Lab (INI-FIOCRUZ)	EDTA	10mL	20			—	_		—	20
HIVPCR viral load	UW-VSL / Peru CTU Laboratory/ CADIG-Immunodiagnostic Lab (INI-FIOCRUZ)	UW-VSL / Peru CTU Laboratory / CADIG-Immunodiagnostic Lab (INI-FIOCRUZ)	EDTA	10mL	—		10	10	10	10	10	50
CD4+T cell count	Local Lab	Local Lab	EDTA	5mL	5		5	5	5	5	5	30
Safetylab												
Hemoglobin	Local Lab	Local Lab	EDTA	5mL	—		—	_	5	5	—	10
Drug levels										******		
VRC01 Ab levels	CSR	NVITAL	SST	8.5mL	8.5		8.5	8.5	8.5	8.5	8.5	51
Immunogenicity & Virologic Assay	/S		******	*******				******		******		
Functional humoral assays ⁶	CSR	HVTN Labs / VRC / NVITAL	SST	8.5mL	17		17	17	17	17	17	102
Viral isolation/sequencing	CSR	TBD	EDTA	10mL	10		10	10	10	10	10	60
Storage												
Serum	CSR		SST	8.5mL	25.5		17	17	17	17	17	110.5
Plasma	CSR		EDTA	5mL	5		5	5	5	5	5	30
PBMC	CSR		ACD	8.5mL	34		_	-	-	34	34	102
Visit total ⁸	1	1	3		128		75.5	75.5	80.5	114.5	109.5	584
56-Day total					128		204	279	360	346	109.5	
URINE COLLECTION					1		1	8	1	ı	8	
Pregnancy Test ⁴	Local Lab	Local Lab			х		_	_	_	x	_	

¹ CSR = central specimen repository; UW-VSL = University of Washington Virology Specialty Laboratory (Seattle, Washington, USA); Peru CTU Laboratory (Lima, Peru); CADIG - Immunodiagnostic Lab (INI-FIOCRUZ) (Rio de Janeiro, Brazil). ² HVTN Laboratories include: South African Immunology, Laboratory-National Institute for Communicable Diseases (SAIL-NICD, Johannesburg, South Africa); Duke University Medical Center (Durham, North Carolina, USA).

Non-HVTN laboratories: NVITAL = NIAID Vaccine Immune T-Cell Antibody Laboratory (Gaithersburg, Maryland, USA; VRC = Vaccine Research Center (Bethesda, Maryland, USA)

TBD = Laboratories to be determined by HVTN Laboratory Program.

³ Local labs may assign appropriate alternative tube types for locally performed tests.

⁴ For persons capable of becoming pregnant, pregnancy test may be performed on urine or blood specimens.

⁵ Visit #.X indicates a Redraw visit where # is a Schedule 1 visit number. Confirmatory draw for HIV diagnostics will be collected at the Redraw visit, in addition to the other indicated specimens. The Redraw visit should occur as soon as possible after the clinic receives a Redraw Request from the HIV diagnostics laboratory. Multiple subsequent Redraw visits may be necessary; only the EDTA blood specimens for HIV diagnostics, viral isolation/sequencing, and plasma storage will be collected at the subsequent Redraw visits. Refer to the HIV Testing SSP for more information.

⁶ Functional humoral assays include nAb, ADCC, virion capture, and phagocytosis assays.

⁷ Date of diagnosis = date of the initial specimen draw that led to the first Redraw Request.

⁸ A 3mL volume is included in the visit totals for drawing a non-additive discard tube to prevent blood tube additive cross-contamination. Refer to the Specimen Collection SSP for more information.

Appendix H Schedule 3—Laboratory procedures for participants discovered to have been HIV-1–infected at enrollment or who become HIV-2–infected

				Visit:	#.X ⁵	Visit:	47	48	
						Days:	D28	D168	
						Weeks after diagnosis ⁷ :	W4	W24	
Procedure	Ship to ¹	Assay location ²	Tube Type ³	Tube size (vol. capacity) ³					Total
BLOOD COLLECTION									
Screening or diagnostic assays									
HIV diagnostics	UW-VSL / Peru CTU Laboratory / CADIG-Immunodiagnostic Lab (INI-FIOCRUZ)	UW-VSL / Peru CTU Laboratory/ CADIG-Immunodiagnostic Lab (INI-FIOCRUZ)	EDTA	10mL	20		_	_	20
HIVPCR viral load	UW-VSL / Peru CTU Laboratory / CADIG-Immunodiagnostic Lab (INI-FIOCRUZ)	UW-VSL / Peru CTU Laboratory/ CADIG-Immunodiagnostic Lab (INI-FIOCRUZ)	EDTA	10mL	—		10	10	20
CD4+T cell count	Local Lab	Local Lab	EDTA	5mL	5		5	5	15
Drug levels									
VRC01 Ab levels	CSR	NVITAL	SST	8.5mL	8.5			_	8.5
Immunogenicity & Virologic Assay	/S								
Functional humoral assays ⁶	CSR	HVTN Labs / VRC / NVITAL	SST	8.5mL	17		_	—	17
Viral isolation/sequencing	CSR	TBD	EDTA	10mL	10		_	—	10
Storage									
Serum	CSR		SST	8.5mL	25.5		17	17	59.5
Plasma	CSR		EDTA	5mL	5			_	5
PBMC	CSR		ACD	8.5mL	34		_	-	34
Visit total ⁸	-				128		35	35	198
56-Day total					128		163	35	
URINE COLLECTION									
Pregnancy Test ^₄	Local Lab	Local Lab			х			—	

¹ CSR = central specimen repository; UW-VSL = University of Washington Virology Specialty Laboratory (Seattle, Washington, USA); Peru CTU Laboratory (Lima, Peru); CADIG - Immunodiagnostic Lab (INI-FIOCRUZ) (Rio de Janeiro, Brazil).

² HVTN Laboratories include: South Africa Immunology Laboratory–National Institute for Communicable Diseases (SAIL-NICD, Johannesburg, South Africa); Duke University Medical Center (Durham, North Carolina, USA); University of Colorado Denver (Denver, Colorado, USA).

Non-HVTN laboratories: NVITAL = NIAID Vaccine Immune T-Cell Antibody Laboratory (Gaithersburg, Maryland, USA); VRC = Vaccine Research Center (Bethesda, Maryland, USA).

TBD = Laboratories to be determined by HVTN Laboratory Program.

³ Local labs may assign appropriate alternative tube types for locally performed tests.

⁴ For persons capable of becoming pregnant, pregnancy test may be performed on urine or blood specimens.

⁵ Visit #X indicates a Redraw visit where # is a Schedule 1 visit number. Confirmatory draw for HIV diagnostics will be collected at the Redraw visit, in addition to the other indicated specimens. The Redraw visit should occur as soon as possible after the clinic receives a Redraw Request from the HIV diagnostics laboratory. Multiple subsequent Redraw visits may be necessary; only the EDTA blood specimens for HIV diagnostics, viral isolation/sequencing, and plasma storage will be collected at the subsequent Redraw visits. Refer to the HIV Testing SSP for more information.

⁶ Functional humoral assays include nAb, ADCC, virion capture, and phagocytosis assays.

⁷ Date of diagnosis = date of the initial specimen draw that led to the first Redraw Request.

⁸ A 3mL volume is included in the visit totals for drawing a non-additive discard tube to prevent blood tube additive cross-contamination. Refer to the Specimen Collection SSP for more information.

Appendix I Schedule 4—Laboratory procedures for participants who discontinue infusions for reasons other than HIV infection

				Visit:	71	72	73	74	75	76	77	78	
				Days after enrollment:	D56	D140	D224	D308	D392	D504	D616	D728	
				Weeks after enrollment:	W8	W20	W32	W44	W56	W72	W88	W104	
								1					
				Tube size									Total
Procedure	Ship to ¹	Assay location ²	Tube Type ³	(vol. capacity) ³									
BLOOD COLLECTION													
Screening or diagnostic assays													
HIV diagnostics ⁵	UW-VSL / Peru CTU Laboratory / CADIG-Immunodiagnostic Lab (INI-FIOCRUZ)	UW-VSL / Peru CTU Laboratory / CADIG-Immunodiagnostic Lab (INI-FIOCRUZ)	EDTA	10mL	10	10	10	10	10	10	10	20 ⁵	90
Safetylabs													
CBC/ Differential	Local lab	Local lab	EDTA	5mL	5	_	5	_	5	_	_	_	15
ALT, Creatinine	Local lab	Local lab	SST	5mL	5	—	5	—	5	—	-	—	15
Drug Levels/Detection				······································									
VRC01 Ab levels	CSR	NVITAL	SST	8.5mL	у	у	у	У	У	У	у	У	0
ARV detection by serum or plasma ⁸	CSR	JHU	SST	8.5mL	у	у	у	У	у	у	у	у	0
ARV detection by dried blood spots	CSR	HVTN Labs	EDTA	2mL	2	2	2	2	2	2	2	2	16
Immunogenicity & Virologic Assays													
Functional humoral assays ⁶	CSR	HVTN Labs / VRC / NVITAL	SST	8.5mL	у	у	у	у	у	у	у	у	0
Viral isolation/sequencing ⁸	CSR	TBD	EDTA	10mL	10	10	10	10	10	10	10	10	80
STORAGE													
Serum storage	CSR		SST	8.5mL	51	42.5	42.5	42.5	42.5	42.5	42.5	42.5	349
PBMC storage	CSR	—	ACD	8.5mL	—	—	—	—	—	—	—	34	34
Visit total ¹⁰					86	68	78	68	78	68	68	112	623
56-Day total					86	68	78	68	78	68	68	112	
URINE COLLECTION													
Urine dipstick ⁷	Local lab	Local lab			Х	—	—	I —	—	—	x	—	
Pregnancy Test ⁴	Local lab	Local lab	1		х	—	Х	 	X	_	X	—	

¹ CSR = central specimen repository; UW-VSL = University of Washington Virology Specialty Laboratory (Seattle, Washington, USA); Peru CTU Laboratory (Lima, Peru); CADIG - Immunodiagnostic Lab (INI-FIOCRUZ) (Rio de Janeiro, Brazil).
 ² HVTN Laboratories include: South African Immunology Laboratory–National Institute for Communicable Diseases (SAIL-NICD, Johannesburg, South Africa); Duke University Medical Center (Durham, North Carolina, USA),; University of Colorado Denver (Denver, Colorado, USA).

Non-HVTN laboratories: NVITAL = NIAID Vaccine Immune T-Cell Antibody Laboratory (Gaithersburg, Maryland, USA); VRC = Vaccine Research Center (Bethesda, Maryland, USA); JHU = Johns Hopkins University, HPTN Laboratory Center (Baltimore, Maryland, USA).

TBD = Laboratories to be determined by HVTN Laboratory Program.

³ Local labs may assign appropriate alternative tube types for locally performed tests.

⁴ For participants capable of becoming pregnant; pregnancy test may be performed on urine or blood specimens.

⁵ At an early termination visit for a withdrawn or terminated participant (see Section 7.12), blood should be drawn for HIV diagnostic testing, as shown for visit 78 above.

⁶ Functional humoral assays include nAb, ADCC, virion capture, and phagocytosis assays.

⁷ And microscopy if needed.

⁸ EDTA blood collected for plasma may also be used for ARV detection assay, if necessary.

⁹ Testing plan for ARV detection to be determined.

¹⁰ A 3mL volume is included in the visit totals for drawing a non-additive discard tube to prevent blood tube additive cross-contamination. Refer to the Specimen Collection SSP for more information.

y = SST blood collected for serum storage will also cover specimen needs for the VRC01 drug level and functional humoral assays; no separate blood draw is needed.

Appendix J Schedule 1—Procedures at CRS for HIV-uninfected participants

∎ ∎ Visit:	1	2	3	4	5	6	7	8	9	10	11	12	13	14	15	16	17	18	19	20	21	22	23	24	25	26	Pos
Day	Screening	D0	D28	D56	D61	D84	D112	2 D140	D168	D196	D224	D252	D280	D308	D336	D364	D392	D420	D448	D476	D504	D532	D560	D616	D672	D728	
Week:		WO	W4	W8		W12	W16	W20	W24	W28	W32	W36	W40	W44	W48	W52	W56	W60	W64	W68	W72	W76	W80	W88	W96	W104	
Procedure	Scr.	Inf#1		Inf#2	2		Inf#3		Inf#4	******	Inf#5		Inf#6	*****	Inf#7		Inf#8		Inf#9		Inf#10						
Study procedures ²									1			0						0									1
Signed screening consent (if used)	х	—	—	—	—	—	—	-	—	—	-	—	—	—	—	—	—	—	—	—	—	—	—	—	—	—	-
Assessment of understanding	Х	—	—	—	—	—	—	-	—	—	—	—	—	—	—	—	—	—	—	—	—	—	—	—	—	—	-
Signed protocol consent	Х	—	—	—	-	-	—	—	-	—	-	—	—	—	-	—	—	—	—	—	—	—	-	—	—	—	-
Medical history	х	-	—	-	-	-	—	-	-	—	-	-	—	—	-	—	-	—	—	-	-	-	-	-	_	—	-
Complete physical exam	х	—	—	—	—	-	—	-	-	—	-	—	—	—	—	—	—	—	—	—	—	—	-	—	—	х	-
Abbreviated physical exam	_	х	—	х	-	-	х	-	х	—	Х	—	х	—	х	—	х	—	х	-	х	-	-	-	_	—	-
Risk reduction counseling	х	х	—	x	-	—	х	-	х	—	Х	—	х	—	х	—	х	—	х	—	х	—	—	—	—	х	_
Pregnancy prevention assessment ³	X	х	—	х	—	—	Х	—	Х	—	Х	—	х	—	Х	—	х	—	Х	—	х	—	—	—	—	Х	-
Confirm eligibility, obtain demographics, randomize	X	—	—	—	—	—	—	-	—	—	 	—	—	—	—	—	—	—	—	—	—	—	—	—	—	—	-
Social impact assessment	_	х	—	X	—	-	Х	-	х	—	Х	—	х	—	Х	—	х	—	х	—	х	—	-	—	—	Х	-
Participant Questionnaire	_	х	—	X	-	-	Х	—	х	—	Х	—	х	—	х	—	х	—	х	—	х	—	-	-	—	Х	-
Concomitant medications	х	х	—	х	-	-	х	-	х	—	Х	—	х	—	х	—	х	—	х	-	х	-	-	-	_	х	-
Intercurrent illness/adverse experience	_	х	—	x	—	-	х	-	х	—	Х	—	х	—	х	—	х	—	х	—	х	—	-	—	—	х	-
HIV infection assessment ⁴	x	х	х	X	x	X	х	X	X	х	X	х	х	х	х	х	х	х	х	х	х	х	x	X	х	х	-
Confirm HIV test results provided to participant ¹²	—	х	х	X	X	X	Х	Х	Х	Х	X	Х	х	Х	Х	Х	х	х	х	х	х	Х	x	X	X	Х	-
ocal lab assessment							8											000000			0						
Screening HIV test	X	—	—	—	—	—	—	-	—	—	 	—	—	—	—	—	—	—	—	—	—	—	—	—	—	—	-
Urine dipstick ¹¹	Х	—	—	х	—	-	—	-	—	—	 	—	—	—	-	—	—	—	—	—	—	—	х	—	—	—	-
Pregnancy (urine or serum HCG) ⁵	х	х	—	x	—	-	х	-	х	—	Х	—	х	—	х	—	х	—	х	—	х	—	х	—	—	—	-
CBC, differential	x	х	—	x	-	-	х	—	х	—	Х	-	х	—	х	—	х	—	х	-	х	-	-	-	_	—	-
ALT, Creatinine	x	х	—	x	-	—	х	-	х	—	Х	—	х	—	х	—	х	—	х	—	х	-	-	—	_	—	-
Syphilis ⁶	—	X ⁷	—	-	—	-	—	-	X ⁷	—	1 –	—	—	—	X ⁷	—	—	—	—	_	X ⁷	—	-	-	—	—	-
Chlamydia, Gonorrhea ⁸	—	X ⁷	—	—	—	—	—	-	X ⁷	—	 	—	—	—	X ⁷	—	—	—	—	—	X ⁷	—	—	—	—	—	-
itudy product administration procedures	0						8											000000000000000000000000000000000000000			0						-
IV infusion ⁹	—	х	—	Х	—	—	X	-	х	—	X	—	х	—	х	—	x	—	х	—	х	—	—	—	—	—	-
Reactogenicity assessment ¹⁰	—	х	—	Х	—	—	x	 	х	—	x	—	х	—	х	—	x	—	х	—	x	—	—	—	—	—	-
Poststudy							00000											0		-	000000000000000000000000000000000000000		-				1
Unblind participant	_	_	_	1-	- 1	—	—	 	-	_	†	_	_	—	 	 	 	_	—	 	—	_	- 1	—	_	_	x

¹ Screening may occur over the course of several contacts/visits up to and including day 0 prior to infusion.

² For specimen collection requirements, see Appendix F.

³ Pregnancy prevention assessments are required only for participants who are capable of becoming pregnant.

⁴ Includes pre-test counseling and HIV testing. A subsequent follow-up contact is conducted to provide post-test counseling and to report results to participant.

⁵ For a participant capable of becoming pregnant, pregnancy test must be performed on the day of infusion prior to infusion. Pregnancy test to determine eligibility may be performed at screening, but must also be done on Day 0 prior to infusion. Presons who are NOT capable of becoming pregnant due to having undergone total hysterectomy or bilateral oophorectomy (verified by medical records), are not required to undergo pregnancy tests may be used to confirm the results of, or substitute for, a urine pregnancy test.

⁶ Syphilis testing will be done by serology.

⁷ Syphilis and Chlamydia/Gonorrhea testing will be performed at visits 2, 9 15, and 21; in addition, testing may occur at any visit or if clinically indicated.

⁸ Chlamydia/Gonorrhea testing will be done with urine and rectal swabs; oropharyngeal swabs will be collected for gonorrhea testing at visit 2; in addition, testing may occur at any visit if clinically indicated. A combination gonorrhea/chlamydia oropharyngeal test is allowable (see the SSP for results reporting).

⁹ Blood draws required at infusion visits must be performed prior to administration of study product; however, it is not necessary to have results prior to administration, except for results of a serum pregnancy test, if indicated. Lab tests must be drawn within the 3 days prior to infusion.

¹⁰ Reactogenicity assessments performed for 3 days postinfusion (see Section 7.10).

¹¹ And microscopy if needed.

¹² If HIV test results are not available at the visit indicated, provide test results at next available opportunity.

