	ndix H Schedule 3—Laboratory procedures for participants discovered to have HIV-1–infected at enrollment or who become HIV-2–infected	
	ndix I Schedule 4—Laboratory procedures for participants who discontinue ons for reasons other than HIV infection	170
Apper	ndix J Schedule 1—Procedures at CRS for HIV-uninfected participants	171
Apper	ndix K Schedule 2—Procedures at CRS for HIV-1-infected participants	172
	ndix L Schedule 3—Procedures at CRS for participants discovered to have bee infected at enrollment or who become HIV-2–infected	
	ndix M Schedule 4—Procedures at CRS for participants who discontinue infusi asons other than HIV infection	
Apper	ndix N Protocol Signature Page	175

1 Overview

Title

A phase 2b study to evaluate the safety and efficacy of VRC01 broadly neutralizing monoclonal antibody in reducing acquisition of HIV-1 infection among men and transgender persons who have sex with men

Primary objectives

- To evaluate the safety and tolerability of VRC01 mAb administered through IV infusion in MSM+TG
- To determine if the VRC01 mAb prevents HIV-1 infection and to estimate the level of efficacy in MSM+TG

MSM = men who have sex with men. TG = male-to-female and female-to-male transgender persons.

Study products and routes of administration

- VRC01: human monoclonal antibody (mAb) VRC-HIVMAB060-00-AB in formulation buffer at pH 5.8 in sufficient normal saline (Sodium Chloride for Injection 0.9%, USP) to be administered at a final volume of 150 mL intravenously (IV)
- Control for VRC01: Sodium Chloride for Injection 0.9%, USP administered at a volume of 150 mL IV

				Infusion schedule (Weeks) [A = VRC01 infusion; C = Control infusion]										
	Treatment	N*	W0	W8	W16	W24	W32	W40	W48	W56	W64	W72	W80 ⁺	W104†
Group 1	VRC01 10 mg/kg	900	А	А	А	А	А	А	А	А	А	А		
Group 2	VRC01 30 mg/kg	900	А	А	А	А	А	А	А	А	А	А		
Group 3	Control	900	с	С	С	С	С	С	С	С	С	С		
	Total: 2700 (900 VRC01 30 mg/kg; 900 VRC01 10 mg/kg; 900 control)													

Table 1-1 Schema

* Due to the randomization scheme, the numbers of VRC01 and control recipients may differ slightly.

• Week 80 is the last study visit for the primary endpoint analysis of prevention efficacy.

* Week 104 is the last study visit for the co-primary endpoint analysis of safety and tolerability.

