2.4.2 Dose and schedule

An equal number of study participants will be randomized to receive VRC01 mAb by IV infusion at a dose of 10 mg/kg or 30 mg/kg every 8 weeks or to receive the control by infusions every 8 weeks. The 8 week infusion interval represents approximately 4 half-lives of the study drug (half-life ~14 days based on previous clinical testing; see the IB).

Infusions will continue for 72 weeks for all groups, with a final primary follow-up visit (without infusion) at week 80 and an additional 24 weeks of follow-up without infusions. Hence, the study duration for each participant is 104 weeks (2 years).

Projected serum concentrations of VRC01 are shown in Figure 2-4. This figure plots predicted median VRC01 serum concentrations over time based on PK models for VRC01 administered at 10 mg/kg every 8 weeks (Panel A) and for VRC01 administered at 30 mg/kg every 8 weeks (Panel B). The plots include shaded regions illustrating time regions where the study participants have serum concentrations in low, medium, and high ranges. Based on in vitro neutralization studies (see Section 2.3) and NHP challenge studies (see Section 2.8.1) and assuming that these accurately predict protection in humans, the expected trough levels of VRC01 are projected to be an order of magnitude higher than the levels required to protect against a majority of circulating HIV-1 strains.

See Section 2.9.3 and Figure 2-9 for VRC01 serum concentrations reported to date for participants administered 10mg/kg and 30mg/kg of VRC01 every 8 weeks in HVTN 104.

10 mg/kg VRC01 group: Predict (50%, 40%, 10%) PYRs in (Low, Medium, High) zones

[figure not shown]

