It is known from published experience with human mAbs directed against the cell surface targets on lymphocytes that infusion of a mAb may be associated with cytokine release. causing a reaction known as cytokine release syndrome [109]. Cytokine release syndrome and other immune reactions such as tumor lysis syndrome have been observed with administration of chimeric and humanized mAb [108]. Most infusion-related events occur within the first 24 hours after beginning administration. Specifically, with regard to cytokine release syndrome reactions, these most commonly occur within the first few hours of beginning the infusion and are more common with the first mAb infusion received. This is because the cytokine release is associated with lysis of the cells targeted by the mAb and the burden of target cells is greatest at the time of the first mAb treatment. With licensed therapeutic mAbs, cytokine release syndrome is managed by temporarily stopping the infusion, administering histamine blockers, and restarting the infusion at a slower rate [110]. Severe reactions such as anaphylaxis, angioedema, bronchospasm, hypotension, and hypoxia are infrequent and more often associated with mAbs targeted to human proteins or with a non-human mAb, such as a murine mAb [108].

Delayed allergic reactions to a mAb may include a serum sickness type of reaction, which is characterized by urticaria, fever, lymph node enlargement, and joint pains. These symptoms may not appear until several days after exposure to the mAb and are noted to be more common with chimeric types of mAb [108]. Serum sickness has not been described with administration of licensed fully human mAbs.

There are several FDA-licensed mAbs for which reactions related to the rate of infusion have been described. Some symptoms may be treated by slowing or stopping the infusion.

Other side effects of licensed mAbs include infections, thrombocytopenia, autoimmune diseases, cancer, dermatitis, and cardiotoxicity [108].

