3.1 Primary objectives and endpoints

Primary objective 1:

To evaluate the safety and tolerability of VRC01 mAb administered through IV infusion in MSM+TG in North America, South America, and Switzerland

Primary endpoint 1:

Local and systemic reactogenicity signs and symptoms, laboratory measures of safety, AEs, SAEs, and rates of discontinuation

Primary objective 2:

To determine if the VRC01 mAb prevents HIV-1 infection and to estimate the level of efficacy in MSM+TG in North America, South America, and Switzerland

Primary endpoint 2:

Documented HIV-1 infection by the Week 80 study visit

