7.4 Post-infusion visits for HIV-uninfected study participants

The following procedures are performed at all post-infusion follow-up visits for HIVuninfected study participants:

- HIV infection assessment including pre-test counseling. A subsequent follow-up contact is conducted to provide post-test counseling and to report results to participant;
- Confirm that participants received HIV test results from previous visit. If not, provide test results and post-test counseling as appropriate;
- Blood collection for HIV testing, PrEP monitoring, and sample storage; and
- Ship samples to HVTN Central Laboratory for HIV diagnostic testing.

Additional procedures will be performed at scheduled follow-up visits as specified in Appendix F and Appendix J:

- Assessment of new or unresolved social impacts (site staff will ask participant about the status of any unresolved social impacts and if s/he has experienced any new social impacts as a result of the trial participation);
- Administration of participant questionnaire, which may include acceptability, behavioral risk, study product belief, motivations, and social impact domains (must be done prior to risk reduction counseling)
- Risk reduction counseling (as described in Section 7.5);
- Urine or serum pregnancy test (for participants who are capable of becoming pregnant). Persons who are NOT capable of becoming pregnant due to having undergone total hysterectomy or bilateral oophorectomy (verified by medical records), are not required to undergo pregnancy testing;
- For participants who are capable of becoming pregnant, pregnancy prevention assessment (as described in Section 7.2 and 7.8);
- Assessment of new or unresolved AEs/intercurrent illnesses;
- Urine dipstick (see Section 7.9); and
- Complete physical examination, including weight, vital signs, and clinical assessments of head, ears, eyes, nose, and throat; neck; lymph nodes; heart; chest; abdomen; extremities; neurological function; and skin.

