7.12 Early termination visit

In the event of early participant termination, site staff should consider if the following assessments are appropriate: a final physical examination, clinical laboratory tests (including urine dipstick, CBC with differential, ALT, and Creatinine), pregnancy testing, social impact assessment, and HIV test.

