Appendix F Schedule 1—Laboratory procedures for HIV-uninfected participants

				Visit	1	2	3	4	5	6	7	8	9	10	11	12	13	14	15	16	17	18	19	20	21	22	23	24	25	26	1
				Day:	Screening	D0	D28	D56	D61	D84	D112	D140	D168	D196	D224	D252	D280	D308	D336	D364	D392	D420	D448	D476	D504	D532	D560	D616	D672	D728	
				Week:	visit ³	W0	W4	W8		W12	W16	W20	W24	W28	W32	W36	W40	W44	W48	W52	W56	W60	W64	W68	W72	W76	W80	W88	W96	W104	
						Inf#1		Inf#2			Inf#3		Inf#4		Inf#5		Inf#6		Inf#7		Inf#8		Inf#9		Inf#10				1		
				Tube size		101#1		1111#2			101#3		101#4		111#5		101#6		IN1#7		101#8		im#9		Int#10						
			Tube	(vol.																											Total
Procedure	Ship to ¹	Assay location ²	Type⁴	capacity) ⁴																							-				
BLOOD COLLECTION							1		1		ĺ																				
Screening/Diagnostic																															
Screening HIV test	Local lab	Local lab	SST	5mL	5	—	-	—	—	—	—	-	—	—	—	-	—	-	—	—	—	—	—	—	—	—	-	—	-	—	5
HIV diagnostics ⁷	Lab (INI-FIOCRUZ)	UW-VSL / Peru CTU Laboratory / CADIG-Immunodiagnostic Lab (INI-FIOCRUZ)	EDTA	10mL		10	10	10	10	10	10	10	10	10	10	10	10	10	10	10	10	10	10	10	10	10	10	10	10	20 ⁷	260
Safety labs	******				• ••• ••• ••• ••• ••• ••• ••• •••																							·			
CBC/ Differential	Local lab	Local lab	EDTA	5mL	5	5	_	5	—	_	5	—	5	—	5	—	5	—	5	—	5	—	5	—	5	—	- 1	-	—	—	55
ALT, Creatinine	Local lab	Local lab	SST	5mL	5	5	—	5	—	_	5	—	5	—	5	- 1	5	—	5	—	5	—	5	—	5	—	-	-	-	—	55
STI Serology	A		.	×	· · · · · · · · · · · · · · · · · · ·				· · · · · · · · · · · · · · · · · · ·																		· · · · · · · · · · · · · · · · · · ·	1			1
Syphilis ¹¹	Local lab	Local lab	SST	5mL	—	5 ¹³	—	—	—	_	—	—	5 ¹³	—	—	- 1	—	—	5 ¹³	—	—	—	—	—	5 ¹³	—	—	-	—	—	20
Drug Levels/Detection		4	 	·																											
VRC01 Ab levels	CSR	NVITAL	SST	8.5mL	-	у	у	у	у	у	у	у	у	у	у	у	у	у	у	у	у	у	у	у	у	у	у	у	у	у	0
ARV detection by serum or plasma ^{9, 11}	CSR	JHU	SST	8.5mL	_	v	v	v	v	v	v	v	v	v	v	v	v	v	v	v	v	v	v	v	v	v	v	v	l v	v	0
ARV detection by dried blood spots 10	CSR	HVTN Labs	EDTA	2mL	_	2	2	2	2	2	2	2	2	2	2	2	2	2	2	2	2	2	2	2	2	2	2	2	2	2	50
Immunogenicity & Virologic Assays				\$		······		·····	*																			******		*	
Host genetics ⁵	CSR	HVTN Labs	ACD	8.5mL	-	z	-	-	—	_	-	_	—	_	- 1	_	—	_	—	_	—	_	—	—	—	—	-	-	-	-	0
Anti-VRC01 Ab levels	CSR	VRC / NVITAL	SST	8.5mL	_	у	_	_	—	_	—	_	_	_	—	у	_	_	_	_	_	_	_	—	_	у	-	-	-	—	0
Functional humoral assays ⁸	CSR	HVTN Labs / VRC / NVITAL	SST	8.5mL	-	у	у	у	у	у	у	у	у	у	у	у	у	у	у	у	у	у	у	у	у	у	у	у	у	у	0

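### After infusion 10, Schedule 1 has no CBC, ALT or creatinine and no adverse-event inquiry until Week 104, although participants attend four visits in between

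*Protocol*

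**What the plan says.** Protocol Section 3.1 defines primary endpoint 1 as "Local and systemic reactogenicity signs and symptoms, laboratory measures of safety, AEs, SAEs, and rates of discontinuation". A footnote to Table 1-1 adds that "Week 104 is the last study visit for the co-primary endpoint analysis of safety and tolerability". Section 2.4.2 gives the timing of treatment: "Infusions will continue for 72 weeks for all groups, with a final primary follow-up visit (without infusion) at week 80".

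The visit schedule for uninfected participants on infusions is Schedule 1, in Appendices F (laboratory) and J (clinic procedures).

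- **AE inquiry.** In Appendix J, "Intercurrent illness/adverse experience" is marked at Weeks 0, 8, 16, 24, 32, 40, 48, 56, 64, 72 and 104. The cells at Weeks 76, 80, 88 and 96 are blank. The concomitant-medication row has the same blanks.
- **Section 7.4.** It does not fill them. AE assessment is in its second list, which opens "Additional procedures will be performed at scheduled follow-up visits as specified in Appendix F and Appendix J".
- **Safety bloods.** In Appendix F, "CBC/ Differential" and ALT/creatinine are drawn at screening and the ten infusion visits. Footnote 9 of Appendix J has blood drawn before study product is given.
- **Urine.** A dipstick is scheduled at screening, Week 8 and Week 80.
- **Early termination.** Section 7.12 says "site staff should consider if the following assessments are appropriate: a final physical examination, clinical laboratory tests". The list goes on to pregnancy, social-impact and HIV testing. It contains no AE assessment.

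**The concern.** The co-primary safety endpoint counts AEs and laboratory measures up to Week 104, but scheduled collection of both thins out after Week 72. The Week 72 blood sample is taken before infusion 10, so it describes nine infusions. The *Infusion #10* row that closes SAP Tables 13A and 13B is therefore a pre-infusion value. Yet Protocol Section 4.13.3.3 and SAP Section 7.1.3 promise laboratory tabulation at every postinfusion timepoint.

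For AEs, a participant who received all ten infusions is asked once in the last 32 weeks. A participant who stopped infusions and moved to Schedule 4 is asked at Weeks 72, 88 and 104 (Appendix M). The more exposed group is questioned less often.

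What is at stake is undercounting of unsolicited AEs after the last infusion, mainly milder or slower events that nobody telephones about. There may also be delay in learning of a related grade 3 or 4 event, which Section 10.3 wants reviewed promptly.

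**Working it through.** **1. Are the laboratory blanks real, or lost when the table was read?** Appendix F prints row and visit totals, which allow a check.

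- CBC/differential: screening plus ten infusion visits = 11 draws; 11 × 5 mL = 55 mL. The printed row total is 55 mL. ALT/creatinine gives the same result.
- Week 72: HIV diagnostics 10 + CBC 5 + ALT/creatinine 5 + syphilis 5 + dried blood spot 2 + viral isolation 10 + serum 42.5 + PBMC 34 + discard tube 3 = 116.5 mL (printed 117).
- Week 76: 10 + 2 + 10 + 51 + 3 = 76 mL (printed 76).
- Weeks 80, 88 and 96: 10 + 2 + 10 + 42.5 + 3 = 67.5 mL each (printed 68).
- Week 104: 20 + 2 + 10 + 42.5 + 34 + 3 = 111.5 mL (printed 112).
- All 26 visit totals rebuild to within rounding, and they sum to the printed 2,062 mL.

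There is no room for a CBC or ALT/creatinine tube after Week 72. The AE row has no totals to check against, but its marks fall on the infusion visits and Week 104, as they do in the concomitant-medication row.

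**2. Spacing of scheduled AE inquiries.** Marked days are 0, 56, 112, 168, 224, 280, 336, 392, 448, 504 and 728. The differences are nine gaps of 56 days and one of 728 − 504 = 224 days. That is 224/7 = 32 weeks, or 32/104 = 31% of follow-up. Visits inside the long gap are Weeks 76, 80, 88 and 96.

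**3. What follows each infusion at 8 weeks.**

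| | AE inquiry | CBC, ALT, creatinine | Urine dipstick |
|---|---|---|---|
| Infusion 1 | Yes | Yes | Yes (Week 8) |
| Infusions 2 to 9 | Yes | Yes | No |
| Infusion 10 | No | No | Yes (Week 80, day 560; 560 − 504 = 56 days) |

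**4. Participants leaving inside the gap.** The inputs are N = 2,700 and 10% annual dropout (Section 4.6.1), taken as a constant rate. HIV infections are ignored and everyone is treated as on Schedule 1.

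- On study at Week 72: 2,700 × exp(−0.10 × 72/52) = 2,351.
- Lost from Week 72 to Week 104: 2,351 × [1 − exp(−0.10 × 32/52)] = 140.
- The same formula gives 76 at 5% per year (the SAP Section 9.5 target) and 193 at 15% (the protocol's sensitivity case).
- VRC01 recipients on study at Week 72: 2,351 × 2/3 = about 1,570. This approximates the number with no CBC, ALT or creatinine scheduled after infusion 10.

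**5. Blood volume of the remedy.** Week 80 would rise from 68 to 78 mL. Its 56-day total would rise from 260 to 270 mL, against the 500 mL limit in Section 9.2.

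**The case against.** The strongest reply is that the schedule is deliberate and other safety information is collected in the gap. Several parts of it stand.

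- **A laboratory test does follow infusion 10.** The Week 80 dipstick is one, and Section 7.12 counts it among clinical laboratory tests. A reader might infer that no safety laboratory test follows the last infusion; that goes too far. At early termination staff are also to consider CBC, ALT and creatinine.
- **The endpoint does not rest on one 32-week recall.** That inference is tempting but wrong. Ten AE assessments cover Weeks 0 to 72. Under Section 7.10 every infusion, including the tenth, has a 3-day reactogenicity period with a staff contact afterwards, and participants are told to call about later events. AE and expedited reporting run for the whole study (Sections 10.2.2 and 10.2.3). Section 8.1 asks about acute-HIV symptoms at every visit.
- **Leavers do not necessarily contribute nothing.** They can still report events through those routes.
- **Late reactions are expected to be uncommon.** Section 2.10 says of serum-sickness-type reactions that "These symptoms may not appear until several days after exposure to the mAb", beyond the 3-day window. It also says serum sickness has not been described with licensed fully human antibodies.
- **Much of the gap is washout.** With a half-life of about 14 days (Section 2.4.2), Week 80 is four half-lives after infusion 10. Laboratory values at that interval already exist for nine infusions.
- **No bias between arms is shown.** The schedule is the same in all three blinded arms, and Section 4.13.3.2 plans no formal AE testing.
- **The Study Specific Procedures are not available here** and may add questions. Section 7.4, however, refers AE assessment to the appendices.

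The blanks at the 4-week and Day 61 visits during the infusion phase are not a defect of the same kind. They lie inside ordinary 8-week intervals, and filling them is a matter of preference.

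None of this supplies the inquiry or the bloods that infusion 10 lacks. The instruction to call covers the time up to the next scheduled visit. After infusion 10 that visit is Week 76, where AEs are not on the schedule.

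**Conclusion.** The point holds for Schedule 1. No CBC/differential, ALT or creatinine is scheduled after infusion 10. No AE inquiry is scheduled between Week 72 and Week 104, a 32-week gap against 8 weeks earlier. In that window unsolicited AEs depend on the reactogenicity contact, spontaneous or expedited reports, and the single Week 104 inquiry. About 140 participants (76 to 193 at 5% to 15% annual dropout) would leave with no scheduled AE inquiry after infusion 10. These counts assume constant dropout and place everyone on Schedule 1, so they are approximate. Schedules 2 and 4 do ask about AEs in this period.

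The likely effect is some undercounting of late AEs in every arm. The documents do not support a claim that the safety comparison is biased between arms or that the endpoint cannot be assessed. This is a cheap improvement to a co-primary endpoint, not a flaw that undermines it.

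**What to change.** - **Appendix J:** mark the AE/intercurrent-illness and concomitant-medication rows at Weeks 76, 80, 88 and 96.
- **Appendices F and J:** mark CBC/differential and ALT/creatinine at Week 80, so that infusion 10 has the same 8-week follow-up as infusions 1 to 9.
- **Section 7.12:** add AE assessment to the early-termination list.
- **SAP Tables 13A and 13B:** add a Week 80 row. This also reconciles the tables with the promised postinfusion tabulation.

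No added AE assessments are needed at the 4-week or Day 61 visits of the infusion phase.

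The cost is an amendment to the appendices, a few minutes at four visits already held, more AE forms under the next-business-day rule of Section 10.2.1, and 10 mL of blood at Week 80. No dose or stopping rule changes.
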